8.4.2. Physical Examination

The investigator or designee will perform a physical examination for all body systems (general appearance, extremities, examination of head, eyes, ears, nose and throat, respiratory, cardiovascular, abdominal, neurological, musculoskeletal, lymphatic and skin assessment) at Screening (Visit 1), end of study Week 24 (Visit 10) and if applicable, OLE Visit 1 and OLE Visit 6.

8.4.3. Clinical Laboratory Assessments

A qualified staff member will collect non-fasting samples for clinical laboratory analysis at screening and baseline and then monthly throughout the study. Samples will be sent to ACM Global Laboratories for analysis. Refer to the study specific laboratory manual for handling and shipping instructions. The following tests will be conducted:

Chemistry Panel	Complete Blood Count
Albumin	Hematocrit
Alkaline phosphatase	Hemoglobin
Alanine aminotransferase (ALT)	Platelet count
Aspartate aminotransferase (AST)	Red blood cell morphology
Blood urea nitrogen (BUN)	Red blood cell count
Bicarbonate	White blood cell count
Calcium	White blood cell differential
Chloride	% & absolute
Creatinine	Basophils
Glucose	Eosinophils
Lactate dehydrogenase (LDH)	Lymphocytes
Phosphorus	Monocytes
Potassium	Neutrophils
Sodium	

Total bilirubin	Urinalysis
Total protein	
Uric acid	
Total cholesterol, LDL, HDL,	
Triglycerides	
Creatine Phosphokinase (CPK)	
Screening Only	
Virology (HepB, HCV, HIV)	
Quantiferon Gold	
Total Iron Binding Capacity (TIBC)	
Serum iron	
Serum Ferritin	
T3/T4, TSH	
Serum pregnancy	

The following clinical laboratory tests: TIBC, serum iron, serum ferritin, T3/T4, TSH are drawn at screening to rule out any underlying conditions that could be causing alopecia. The results of the clinical laboratory tests will be reported on ACM Global Laboratory's standard reports. The investigator must note NCS or CS to define the clinical relevance of any result that is outside the normal range for the laboratory. The investigator must date and initial every laboratory report. The investigator or subinvestigator must review all the Screening (Visit 1) laboratory test results against the study entry criteria for each subject prior to Baseline (Visit 2). The investigator must report all laboratory results that are BOTH outside the normal range for the laboratory AND, in the opinion of the investigator, CS as medical history if found prior to the first study medication treatment or as an AE if found after the first study medication treatment begins. Throughout the study, the investigator must review all laboratory reports in a timely manner.

8.4.4. Pregnancy tests

Subjects who are WOCBP must have a negative serum pregnancy test result at Screening (Visit 1) to continue in the study, and a negative UPT at Baseline (Visit 2) prior to randomization. In addition, the investigator or designee will perform a urine pregnancy test for subjects who are WOCBP at monthly visits during the double-blind portion of the study and during the OLE at OLE Visit 1 (if Visit 28 > 30 days from entry to OLE), and OLE 2-6. The UPT kits provided by ACM Global Laboratories have a minimum sensitivity of 25-mIU β -HCG/milliliter (mL) of urine. If the result of any post-treatment urine pregnancy test is positive, the subject will be withdrawn from the study and the subject's pregnancy documented and followed.

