5.5. Open-Label Extension

At Week 24 (Visit 10) or Week 28 (Visit 11), the subject may be given the option to move into the OLE treatment if the subject meets the OLE entry criteria in Section 5.5.1.

- If the subject declines the OLE, Visit 11 (Post-treatment) will be the last double-blind study visit.
- If the subject chooses to continue into the OLE, she/he must sign an OLE ICF/Accent, complete Visit 10 or Visit 11, as appropriate, and OLE Visit 1, prior to being dispensed open-label drug and receiving continued study medication application instructions. The subject will be scheduled for OLE Visit 2.
- If the subject enrolls in open-label treatment within 30 days of completion of Week 24 (Visit 10) or Week 28 (Visit 11), OLE Visit 1 will be conducted to obtain consent/assent and perform the procedures in the Schedule of Assessments. This will be considered the official date that the subject initiated OLE treatment.
- If the subject enrolls in open-label treatment > 30 days after completion of Week 28, OLE Visit 1 will be conducted in order to obtain consent/ assent, and complete the procedures detailed in the Scheduled of Events. This will be considered the official date that the subject initiated OLE treatment and the scheduling of subsequent visits will be based on this date.

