5.5.1. OLE Entry Criteria

1. Subject must be able to comprehend and willing to sign the OLE Informed Consent/Accent Form (ICF).
2. Subject must continue to meet the entry criteria from the double-blind period. The SALT score and duration of disease are based on the double-blind period baseline visit.
3. Subject has not experienced any clinically significant AEs, SAEs or tolerability issues that met the study discontinuation criteria in the double-blind period.
4. Subject is capable of regrowing scalp hair in the opinion of the investigator.
5. WOCBP must have a negative UPT at entry into OLE.

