Schedule Telephone Call to occur the Day Prior to Visit 5, and Visit 10 ²⁰				X					X		

Open-Label Extension	Open-Label Treatment						Post-Treatment	
	OLE Visit 1		OLE Visit 2	OLE Visit 3	OLE Visit 4	OLE Visit 5		
Week	OLE Visit 1 occurs at Visit 10 or 11	Visit 11 (Week28) was:		2	4	12	24	28
Treatment Day		≤ 30 Days	> 30 Days	15	29	85	169	197
Treatment Window(days)	NA	NA	NA	± 3	± 3	± 7	± 7	± 7
Informed Consent/ Assent	X	X	X					
Inclusion/exclusion criteria	X	X	X					
Physical exam ²			X					X
Medical History Update			X					
Vital signs ³		X	X	X	X	X	X	X
Clinical CBC, Chemistry, Virology, Serum Pregnancy, Urinalysis ⁴			X	X	X	X	X	X
Urine pregnancy test ⁵		X	X	X	X	X	X	X
ECG								X
SALT Score (prior to ALODEX) ⁶		X ¹⁵	X		X	X	X	X
ALODEX Score (after SALT) ⁷		X ¹⁵	X		X	X	X	X
Alopecia Appearance Assessment (AAA): Clinician Rating (CR)						X	X	X
All Patches, Target Patch								
Alopecia Appearance Assessment (AAA): Subject Rating (SR)						X	X	X
All Patches, Target Patch								
Subject Global Impression Treatment Satisfaction (SGITS)						X		
Photography (complete scalp and target patch)			X ¹⁵		X	X	X	X
Subject instructions ¹¹	X	X	X	X	X	X		
Dispense and weigh study medication ¹²	X	X	X	X	X	X (Weigh only)		
Collect study medication, assess compliance			X	X	X	X		
Concomitant therapies			X	X	X	X	X	X
Adverse events			X	X	X	X	X	X

¹A written, signed ICF/ assent must be obtained from each subject prior to performing any study related procedure (i.e., prior to performing vital signs, standardized photography, biopsies, clinical laboratory sampling or urine pregnancy tests.) An OLE ICF must be obtained prior to performing any OLE assessments.

² A physical exam includes: general appearance, extremities, examination of head, eyes, ears, nose and throat, respiratory, cardiovascular, abdominal, neurological, musculoskeletal, lymphatic and skin assessment.

³Vitals signs include: oral or ear temperature, blood pressure, heart rate, respiration rate (height and weight at baseline only).

⁴ Clinical laboratory sampling include: CBC, Chemistry with lipids, Urinalysis. Quantiferon Gold, HIV, Hepatitis B and C, and Serum Pregnancy should be done at screening visit only.

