
⁵ UPT must be performed in WOCBP prior to randomization at Baseline (Visit 2) and must be negative for the subject to continue in the study. UPTs in WOCBP must also be obtained at Visits 5, 6, 7, 8, 9, 10, 11 and if applicable, OLE Visit 1, and OLE Visit 2-6. WOCBP must have a negative serum pregnancy test at Screening (Visit 1) and a negative UPT at baseline (Visit 2) prior to randomization. WOCBP must have a negative UPT prior to continuation into the OLE.

⁶ SALT score must be determined prior to ALODEX using device provided. At Baseline (Visit 2), SALT score should be determined prior to application of study medication.

⁷ ALODEX score determined after SALT score using device provided. At Baseline (Visit 2), ALODEX score should be determined prior to application of study medication.

⁸ The subject will be instructed to identify the most bothersome patchy area- this will be the Target Patch. At Baseline (Visit 2), the Target Patch should be identified prior to application of study medication.

⁹ The investigator will assess active hair loss through the hair pull test and the presence of exclamation point hairs. At Baseline (Visit 2), the assessment should be determined prior to application of study medication.

¹⁰ At Baseline (Visit 2), study assessments must be performed prior to application of study medication.

¹¹ The study staff must instruct the subject to apply study medication according to the instructions in APPENDIX 1, 2 and 3.

¹² The study staff must weigh the study medication bottle(s) with cap prior to dispensing to the subject and after the study medication bottles are returned to the investigational site. Staff should review the usage based on the weight of the bottle and counsel the subject as necessary.

¹³ At Baseline (Visit 2), the first application of study medication should be performed by the subject under the supervision of the study staff and the subject should be observed for 20 minutes after the initial application.

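### Protocol 8.4.4 limits the OLE Visit 1 pregnancy test to gaps of more than 30 days, contradicting OLE entry criterion 5 and the OLE schedule, and counts the gap from a visit that does not exist

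*Protocol*

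**What the plan says.** Four places in the protocol govern this test, and the SAP repeats one of them.

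- **Protocol 8.4.4 (Pregnancy tests)** schedules it "during the OLE at OLE Visit 1 (if Visit 28 > 30 days from entry to OLE), and OLE 2-6". OLE Visit 1 therefore carries a test only after a gap of more than 30 days.
- **Protocol 5.5.1, item 5**, repeated in the synopsis, reads "WOCBP must have a negative UPT at entry into OLE". It sets no gap condition.
- **Protocol 6.3, OLE schedule**, row "Urine pregnancy test", is marked at OLE Visit 1 in both the up-to-30-days and the over-30-days columns. It is blank only where OLE Visit 1 is the same visit as Visit 10 or 11. SAP 1.2 has the same pattern.
- **Protocol 6.3, footnote 5**, says tests "must also be obtained at Visits 5, 6, 7, 8, 9, 10, 11 and if applicable, OLE Visit 1, and OLE Visit 2-6", and adds "WOCBP must have a negative UPT prior to continuation into the OLE".

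Protocol 5.5 describes two routes into the extension on a separate day. One begins "If the subject enrolls in open-label treatment within 30 days of completion of Week 24 (Visit 10) or Week 28 (Visit 11"; the other begins "If the subject enrolls in open-label treatment > 30 days after completion of Week 28". In both, OLE Visit 1 is held and the scheduled procedures are carried out.

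**The concern.** A woman of childbearing potential may return for OLE Visit 1 on a separate day, within 30 days of her last double-blind visit. The schedule and criterion 5 require a pregnancy test at that visit; 8.4.4 does not. If the site works from 8.4.4, she can receive open-label drug without the test that criterion 5 demands. That would be an eligibility violation and a possible exposure in pregnancy. Under 8.4.4 her next test would be at OLE Visit 2, Day 15 ± 3, which is Day 12 to Day 18 of the extension.

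The 8.4.4 condition is also hard to apply. There is no Visit 28; Week 28 is Visit 11. The synopsis expressly asks for Visit 11 only from subjects who decline the OLE or are not eligible for it. Someone who enters from Visit 10 may therefore have no such visit to count from.

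**Working it through.** The plan states no figure to reproduce. The check compares the texts and counts days.

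**Step 1. Does the conflict survive the layout?** In the protocol's OLE schedule, the clinical laboratory row directly above the pregnancy test is blank under up-to-30-days and marked under over-30-days. The pregnancy test row is marked under both. The schedule thus separates procedures needed only after a long gap from those needed after either gap, and puts the pregnancy test in the second group. The SAP copy shows the same contrast between the two rows, so an extraction fault is unlikely.

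**Step 2. The rules side by side, for a woman of childbearing potential.** Visit 28 is read as Week 28, because footnote 15 of the schedule uses Week 28 for its own 30-day condition at OLE Visit 1.

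| Entry to the OLE | 8.4.4: test at OLE Visit 1? | Criterion 5 | Schedule |
|---|---|---|---|
| Same visit as Visit 10 or 11 | No separate test | Negative test at entry; that visit's own test serves | Blank at OLE Visit 1; test marked at Visits 10 and 11 |
| Separate day, no more than 30 days after Week 28 | No | Negative test at entry | Test marked |
| More than 30 days after Week 28 | Yes | Negative test at entry | Test marked |

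Only the middle row conflicts.

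**Step 3. Age of the last test if 8.4.4 alone is followed.** Age = day of OLE Visit 1 minus day of the last double-blind test. Nominal days from the double-blind schedule: Visit 10 = Day 169, Visit 11 = Day 197. No unscheduled test is assumed.

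- Same-day entry: 0 days.
- Visit 11 held: no test is called for through Day 197 + 30 = Day 227, so the age is at most 227 − 197 = 30 days.
- Visit 11 not held, entry within 30 days of Visit 10: latest day 169 + 30 = Day 199, so the age is at most 199 − 169 = 30 days.
- Visit 11 not held, gap counted from nominal Week 28: no test through Day 227, so the age is at most 227 − 169 = 58 days.
- Entry after Day 227: tested at OLE Visit 1, so 0 days.

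**Step 4. The reference visit is itself unsettled.** For the short gap, Protocol 5.5 counts from Visit 10 or Visit 11; for the long gap, from Week 28 only. The schedule's two gap columns are headed by Visit 11. SAP 1.1 counts its over-30-days gap from Visit 10 or Visit 11. The difference between 30 and 58 days comes from this choice.

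**The case against.** The strongest reply is that the documents already control entry. Protocol 6.2 has assessments performed as the Section 6.3 schedule sets out. For the short-gap route, Protocol 5.5 says OLE Visit 1 is held to carry out the scheduled procedures. That schedule marks both the pregnancy test and an eligibility check in the up-to-30-days column. To miss the test, a site would have to act on one parenthesis and overlook 6.2, 5.5, criterion 5 and the schedule. This stands, and it makes the consequence conditional. It does not remove the contradiction.

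A reader might infer that footnote 5 also contradicts 8.4.4. It does not do so by itself. It lists OLE Visit 1 only where applicable, and a negative result at Visit 10 or 11 can count as coming before continuation.

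The protocol also gives reasons not to overstate the exposure risk. Double-blind tests from Week 4 onward are 28 days apart nominally, and up to 28 + 3 + 3 = 34 days with the visit windows. OLE tests are further apart: 85 − 29 = 56 days between OLE Visits 3 and 4, and 169 − 85 = 84 days between OLE Visits 4 and 5. Protocol 10.2 requires highly effective contraception during the study and for 30 days after the last application. A test 30 days old is therefore not unusual by the protocol's own spacing. These intervals concern monitoring during treatment, however; they do not meet a criterion that asks for a negative test at entry.

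**Conclusion.** The contradiction is real: 8.4.4 cannot be reconciled with criterion 5 or with the schedule row for entry on a separate day up to 30 days after Week 28. Same-day entrants and those with longer gaps are unaffected.

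Two stronger readings are tempting. One is that the plan lets open-label treatment begin on an old test. The documents do not support that as a general statement, because 6.2 and 5.5 direct sites to a schedule that includes the test; it follows only if 8.4.4 is used alone. The other is that 30 days is the limit on the age of the last test. That holds if Visit 11 took place, or if the gap is counted from Visit 10. It rises to 58 days at nominal visit days if Visit 11 was not held, the gap is counted from Week 28 and no unscheduled test was done.

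The number of women affected cannot be derived from the documents. No double-blind endpoint or analysis depends on the point. It is an internal inconsistency in an eligibility and pregnancy-exposure safeguard, and should be corrected for that reason.

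**What to change.** Reconcile Protocol 8.4.4, entry criterion 5 (synopsis and 5.5.1), the OLE schedule and footnote 5 in Protocol 6.3, and the schedule copy in SAP 1.2, so that all state one condition for the pregnancy test at OLE Visit 1. The sponsor's clinical team should choose the condition; this review does not say which is right. Replace Visit 28 in 8.4.4 with a defined reference visit that also works for subjects who enter from Visit 10 without a Visit 11, and use the same reference in Protocol 5.5 and the schedule's column headings.

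The cost is a short text correction in the protocol, with a matching check of the SAP copy. No statistical analysis changes. Whether any procedure is added or removed depends on the condition chosen.

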8.4.5. ECGs

Standard 12-lead ECGs will be performed by a qualified staff member at Screening (Visit 1), Baseline (Visit 2), Day 15 (Visit 4) and monthly visits during the double-blind period study and if subject is continuing in the OLE, at OLE Visit 6. The ECGs must be obtained using a standard 12-lead ECG with a 10mm/mV amplitude, at 25mm/sec and a 5 to 10-second duration. To ensure a steady heart rate the subject must rest quietly in the supine position for at least 5 minutes prior to performing the ECG.

A central lab, eResearch Technology, Inc. (ERT), will provide ECG equipment, supplies and site training. In addition, ERT will process ECGs received by the sites and report results via a secure study portal. The ECG results will be interpreted by a qualified health professional (evaluator) and the interpretation reported either directly on the tracing or in a separate report. The evaluator will interpret the results of every ECG and define the ECG as “normal” or “abnormal”. Variations such as minor ST changes (*i.e.*, <0.5mm depression) and early re-polarization are considered normal.

The investigator must review the evaluator’s interpretation of each subject’s screening ECG prior to Baseline (Visit 2). The investigator will review the evaluator’s interpretation of all ECG reports in a timely manner and comment on the clinical relevance of any result that is defined by the evaluator as abnormal.

Any abnormalities that are, in the opinion of the investigator, clinically significant, must be reported as history if found prior to the start of the first study medication application or as an AE if found after the start of the first study medication application (see Section 9.1.1).

8.5. Other Assessments

8.5.1. Demographics, Medical History and Alopecia Areata History

During the screening visit, the investigator or designee will interview each subject to obtain demographic information including date of birth, sex at birth, Fitzpatrick skin type, race and, if appropriate, ethnicity. The investigator or designee will interview each subject to obtain medical history information related to all medical conditions, surgeries and disease states that, at screening: are ongoing, require concomitant therapy or are, in the opinion of the investigator, relevant to the subject’s study participation. In addition, the medical history of women who are not of childbearing potential should reflect the reason *e.g.* post-menopausal for 1 year or greater, bilateral tubal ligation, or hysterectomy. The investigator or designee will also obtain an AA history at screening (APPENDIX 2).

8.5.2. Photographic Assessment

A qualified investigational staff member will take standardized photographs of the scalp at baseline and then monthly during the double-blind period and if the subject is continuing in the OLE, OLE Visits 3-6 and OLE Visit 1 (according to the Schedule of Assessments), if there is a significant change from the last double-blind study visit. The photographs are to document the baseline hair loss and hair growth during treatment. In addition, a target patch will be identified and photographed. Equipment, supplies, training and detailed instructions for obtaining and managing photographs will be provided by Canfield Scientific to the investigational center prior to the initiation of subject enrollment.

9. ADVERSE EVENTS

Adverse events will be monitored throughout the study and reported on the appropriate Aclaris Therapeutics, Inc. AE eCRF.

9.1. Definitions

9.1.1. Adverse events (AE)

An AE is any untoward medical occurrence in a subject administered a study medication(s) and which does not necessarily have a causal relationship with the study medication. An AE can therefore be any unfavorable and unintended sign or symptom associated with the use of a study medication (including an abnormal laboratory finding), whether or not related to the study medication.

Thus, any new, clinically significant worsening of an existing sign, symptom or disease, should be considered an AE.

Every new episode or clinically significant worsening of a chronic condition (e.g., headaches, seasonal allergies, depression, or hypertension) should be reported as a separate AE, even if the condition is reported in the subject's medical history.

The investigator should, when certain, report a diagnosis rather than the signs, symptoms or clinically significant abnormal laboratory values associated with the AE. Otherwise, signs, symptoms or abnormal laboratory values may be used to describe the AE.

Any CS abnormality discovered prior to the first study medication treatment should be reported as medical history, not as an AE.

9.1.2. Serious adverse event (SAE)

A Serious Adverse Event is any untoward medical occurrence that at any dose:

- Results in death
- Is life threatening
- Requires inpatient hospitalization or prolongation of existing hospitalization
- Results in persistent or significant disability/incapacity, or
- Is a congenital anomaly/birth defect
- Is an important medical event.

The term "life threatening" refers to an event in which the subject was at risk of death at the time of event; it does not refer to an event that hypothetically might have caused death if it were more severe.

Inpatient hospitalization is considered to have occurred if the subject is admitted to the hospital on an in-patient basis, even if released the same day. Prolongation of hospitalization is defined as an additional night stay in the hospital. Hospitalization for a diagnostic test (even if related to an AE) or elective hospitalization that was planned before study enrollment (signing the ICF) are not themselves reasons for an event to be defined as a SAE.

Important medical events are those that may not be immediately life threatening, result in death or hospitalization, but are clearly of major clinical significance and may jeopardize the subject or require intervention to prevent one of the outcomes listed in the SAE definition above. These should also usually be considered serious. Examples of such events are intensive treatment in an

emergency room or at home for allergic bronchospasm, blood dyscrasias or convulsions that do not result in hospitalization.

9.1.3. Unexpected adverse event

An AE is considered unexpected if it is not listed in the Investigator Brochure or is not listed at the specificity or severity that has been observed.

9.1.4. Adverse event reporting period

The investigator must start reporting non-serious AEs with the subject's first study medication application and continue reporting until the end of the subject's last study visit. Reporting for SAEs must start when the subject signs the ICF and continue until the end of the subject's last visit.

